for Bell's palsy was not published until 2014 (4). It was a randomized control trial that divided patients into standard treatment (oral steroids and acyclovir) versus standard treatment with intratympanic steroid injection. There was not a statistically significant difference between the complete recovery rate of the control group and of the intratympanic steroid group; however, the time to recovery was significantly shorter in the intratympanic steroid injection group as compared to the control group. Limitations of this study include small sample size and high attrition rate.

There have not been any other studies published in the literature looking at improving facial nerve recovery in idiopathic facial nerve paralysis with the use of intratympanic steroid injections.

5. Trial Objectives and Purpose

The question proposed by this study are:

Does intratympanic steroid injection improve the complete recovery rate of patients with idiopathic facial nerve paralysis?

Does intratympanic steroid injection hasten the time to recovery in patients with idiopathic facial nerve paralysis?

Are there significantly more adverse effects with the use of intratympanic steroid injection as compared to oral steroids in patients with idiopathic facial nerve paralysis?

The trial seeks to provide evidence that intratympanic steroid injection are acceptable and successful adjuncts to treatment of idiopathic facial nerve paralysis.

To answer this question, a prospective, single-blinded, randomized trial will be performed. The subjects will be randomized into the treatment group and the control group. The control group will receive oral steroids which is the current standard of care. Patients in the treatment group will receive oral steroids AND intratympanic steroid injections. The patient's will not be blinded because the patient will be undergoing an in-office procedure. It has been found to be unethical to perform sham procedures in patients. A third group of patients will consist of those patients that are unable to take oral steroids for medical reasons. These patients will only receive the intratympanic injection and they are placed in this group for medical reasons only (no randomization into this group). The patients will be examined and scored using House-Brackmann scoring system by a blinded investigator trained in otolaryngology.

6. Trial Design

Design:

Prospective, randomized, single-blinded clinical trial

Protocol: *Facial Nerve Study*

PI: [name]

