End Points:

Complete recovery of facial nerve function

Time to complete recovery of facial nerve function

Improvement of facial nerve function within 3 weeks

Time to initial improvement of facial nerve function

Adverse effects related to the treatment

Methodology:

Screening

Patients age 18-99 will be identified in clinic as having an acute facial nerve paralysis of H-B IV or greater. Symptoms must have developed within a 72 hour period and be present for the last 21 days or less.

Baseline assessment

Patients who meet criteria will undergo a complete history, head, neck, and cranial nerve exam. Facial function will be evaluated with H-B scoring system. In patients where there is a suspicion of Lyme disease, Lyme disease serology will be performed. Electroneurography (ENoG) and electromyography (EMG) testing will be performed on patients with complete paralysis only.

Treatment Phase

Participants in groups 1 & 2 will be treated with steroids (prednisone 60 mg for 5 days followed by a 5 day taper). Patients will then be randomized into either control group (Group 1) or treatment group (Group 2). Patients in Group 2 will undergo intratympanic steroid injection. An audiogram and tympanography testing will be performed prior to injections.

Participants unable to take oral steroids for medical reasons (such as diabetes) will be placed in Group 3. These participants will receive intratympanic steroid injections only. An audiogram and tympanography testing will be performed prior to injections.

Injection will be up to 1cc of dexamethasone 24mg/mL. The procedure will be performed at supine position under a microscope. Local anesthesia will be achieved with topical phenol. A myringotomy will be made in the tympanic membrane. A 1 mL syringe connected to a needle will be used to slowly inject between 0.2 cc and 1.0 cc of solution through the myringotomy, with the subject's head turned 45 degrees to the opposite side. The subject will be asked to maintain positioning for at least 30 minutes and refrain from swallowing. The dose administered will vary due to subject-specific factors.

Follow-Up

Patients will be evaluated once a week for the first month after completion of treatment. From that point, patients will be evaluated monthly until complete recovery.

Procedures:

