Participants are identified in clinic to have idiopathic facial nerve paralysis. If they meet inclusion criteria, they will then be asked to participate in the study and sign the consent form. Participants will undergo a complete medical history including facial nerve paralysis history, head, neck, and cranial nerve exam. Facial function will be evaluated with H-B scoring system. Lyme disease serology will be drawn on patients for which there is a suspicion of Lyme disease (SOC). Electroneurography (ENoG) and electromyography (EMG) testing will be performed only on patients with complete paralysis, as part of the standard of care (SOC) work-up. Next, patients in Groups 1 & 2 will be prescribed a course of oral prednisone. They will be randomized to Group 1 or Group 2. If randomized to Group 1, patient will come back weekly for a month for evaluation of facial nerve function. If randomized to Group 2 or placed into Group 3, patients will undergo an audiogram and tympanometry testing, which is SOC prior to any intratympanic injection. Patients will undergo intratympanic steroid injection to affected side after all details and risks of each procedure are discussed. There will be one injection every 3-7 days over the course of 3 weeks for a total of 3 injections. Follow-up will be once a week for the first month after the completion of treatment. From that point, patients will be evaluated monthly. All patients Group 2 & 3 will undergo a post-procedure audiogram and tympanogram approximately 1 month following the 3rd injection, which is SOC. Follow-up will be completed once full facial nerve recovery to H-B I or for up to one year, whichever comes first. At each clinic visit patients will undergo a complete head and neck exam, including H-B score. Extensive review of systems will be completed at every visit. Facial nerve exams will be video recorded pre-treatment and all post-treatment follow-up visits to allow for 2 independent blinded reviewers to determine facial nerve recovery and H-B score; a third unblinded review will be performed by the treating physician.

Adverse effects of the treatment will be assessed at each visit.

7. Selection and Withdrawal of Subjects

Inclusion Criteria:

1. 18 to 99 years
2. English as primary language
3. Acute unilateral facial palsy without skin lesions which developed within a 72-hour period and is present for 21 days or less.
4. Moderate to severe facial palsy [House-Brackmann grade IV or greater]

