Efficacy of the treatment will be assessed by measuring facial nerve function using the H-B scale I-VI. Two blinded trained otolaryngologist or mid-level provider trained in otolaryngology will determine the efficacy by evaluating each individual study subject via video recording.

10. Assessment of Safety

Risks of intratympanic steroid injections include pain, bleeding, vertigo, otitis media, and tympanic membrane perforation.

The presence or absence of tympanic membrane perforation will be documented at 14 days and 1 month post-treatment. If a perforation is present, the extent of the perforation, type of treatment, and when resolved will be recorded.

All adverse events will be reported to the IRB and the Otolaryngology Department Quality Assurance. Admission of a trial participant to an emergency room or hospital will be recorded.

11. Statistics

A sample calculation was performed for the number of subjects to be enrolled in order to prove superiority of oral steroids + intratympanic steroids over oral steroids alone. The assumption was made that a 20% increase in primary outcome of complete recovery would be significant. A sample size of 25 subjects should detect a difference at a power greater than 80% and an alpha of 0.05. To account for potential testing or data collection errors, we will collect data on 30 subjects treated with oral steroids and intratympanic steroid injections, as well as 30 controls treated with oral steroids only, for a total of 60 subjects. Data will be collected on up to 30 additional subjects that are placed into Group 3 for medical reasons; therefore total number of subjects to be recruited is 90.

12. Direct Access to Source Data/Documents

The investigators will permit study-related monitoring, audits, IRB/IEC review, and regulatory inspection(s) by providing direct access to source data/documents.

13. Quality Control and Quality Assurance

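### The only listed safety end point is limited to treatment-related effects, with no assessor or criteria for relatedness, so injection-like complaints may be counted more readily in Group 2 than in Group 1

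*Combined protocol and SAP*

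**What the plan says.** - **Section 6, End Points.** Five end points are listed. The only one on safety is "Adverse effects related to the treatment".
- **Section 6, Procedures.** The visit instruction has the same scope: "Adverse effects of the treatment will be assessed at each visit". The same section also states "Extensive review of systems will be completed at every visit".
- **Section 5.** The third study question is broader: "Are there significantly more adverse effects with the use of intratympanic steroid injection as compared to oral steroids in patients with idiopathic facial nerve paralysis". It carries no relatedness limit.
- **Section 10, Assessment of Safety.** Pain, bleeding, vertigo, otitis media and tympanic membrane perforation are listed as risks of the injection. Perforation is to be documented as present or absent at 14 days and 1 month. For reporting: "All adverse events will be reported to the IRB and the Otolaryngology Department Quality Assurance".
- **Blinding.** Section 5 says "The patient's will not be blinded because the patient will be undergoing an in-office procedure". The videos in section 6 are for "2 independent blinded reviewers to determine facial nerve recovery and H-B score", and "a third unblinded review will be performed by the treating physician".
- **Treatment (sections 6 and 8).** Groups 1 and 2 both receive oral prednisone. Only Group 2 of the randomised arms receives injections.

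No section says who decides whether an event is related, by what criteria, or whether that person knows the arm.

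**The concern.** Read literally, the end point removes events judged unrelated before the arms are compared. That is harmless only if the judgement works the same way in both arms, and here there is reason to expect that it will not. Ear pain or dizziness raised in a Group 2 patient has an obvious candidate cause, named in the plan. The same complaint in a Group 1 patient has none. Equal visit schedules would not remove this difference.

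The third study question, and the stated purpose of showing that injections are acceptable, depend on this comparison. Uneven attribution could produce an apparent excess in Group 2 that the injection did not cause. It could also hide a real excess, if an unblinded physician tends to call events unrelated. Section 13 defends the data, despite incomplete blinding, by pointing to objective measures. All four measures it names concern facial recovery, so that defence does not reach the safety end point.

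**Working it through.** **1. Scope.** The end-point list and the visit instruction (section 6) cover effects of the treatment. The study question (section 5) covers adverse effects generally. The reporting rule (section 10) covers all adverse events, but it governs what goes to the IRB and quality assurance, not what is compared. The compared set is therefore narrower than the question, and nothing in the plan reconciles the two.

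**2. Who judges.** Patients know their arm and the treating physician's review is called unblinded. Every blinded role (sections 5, 6 and 10) concerns House-Brackmann score or facial recovery. No blinded adverse-event assessor is named. That relatedness will be judged by someone who knows the arm is an inference, though a strong one.

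**3. Which events are exposed.** Pain, vertigo and otitis media are listed as risks of the injection only, so they are the most exposed. Systemic complaints are less so, because prednisone is given in both arms. Perforation is little exposed, because it is documented at fixed times.

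**4. Illustration of size.** The plan gives no safety figure to reproduce. From the plan: 30 per arm (section 11). Assumed, because the plan gives none: the background complaint rate r, equal in both arms (no true excess); the share of complaints labelled related, q1 in Group 1 and q2 in Group 2; and a two-sided Fisher exact test at 0.05.

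A participant is counted with probability r × q1 in Group 1 and r × q2 in Group 2. The false-difference rate is the sum, over all pairs of counts (a, b), of Bin(a; 30, r·q1) × Bin(b; 30, r·q2) for the pairs where Fisher p ≤ 0.05.

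Example: r = 20%, q1 = 25%, q2 = 80%. The expected counts are 30 × 0.20 × 0.25 = 1.5 and 30 × 0.20 × 0.80 = 4.8, and the false-difference rate is 12%.

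| Attribution, Group 2 v Group 1 | r = 10% | 15% | 20% | 30% |
|---|---|---|---|---|
| 80% v 25% | 1.5% | 5.5% | 12% | 28% |
| 80% v 50% | 0.7% | 2.2% | 3.9% | 7.8% |
| All events counted | 0.9% | 1.7% | 2.2% | 2.6% |

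At r = 10% the 80% v 50% figure is below the all-events figure. Filtering leaves few events, and Fisher is very conservative with few events.

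**5. Extreme bound.** Suppose every complaint is attributed in Group 2 and none in Group 1. Fisher then needs 6 v 0 (p = 0.024), since 5 v 0 gives p = 0.052. P(Bin(30, r) ≥ 6) is 7%, 29% and 57% at r = 10%, 15% and 20%. This is an upper bound, and for local injection-like complaints only.

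**The case against.** The strongest reply is that the plan describes no causality step at all. The end-point bullet is five words, the study question has no relatedness limit, and section 10 speaks of all adverse events. The bullet might be loose wording for events arising during treatment. This stands in part: the attribution step and its assessor are inferred. But the visit instruction repeats the limit, and nothing in the plan makes all events the compared set, so a team following the text as written would filter.

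Second, Group 1 does receive a treatment. A reader might infer that the filter must differ between arms by its very construction, with nothing countable in Group 1, and take 7%, 29% and 57% as the size of the problem. The plan does not support that. Prednisone complaints can be called related in either arm, and all-v-none attribution fits local complaints at most.

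Third, with milder asymmetry (80% v 50%) the false-difference rate stays below 5% up to a 20% background rate. The test is also an assumption, and it matters. At 80% v 20% attribution and a 20% background rate, Fisher gives 14.6% and an uncorrected chi-square gives 36.4%. Both points stand.

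Fourth, a reader might infer from section 10 that every event is already held as analysable data. The section says only that events are reported; systematic capture in both arms is not established.

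**Conclusion.** The concern holds in a limited form. The listed safety end point is narrower than the question it serves, and the judgement that defines it has no named assessor, no criteria and no blinding. Followed as written, it can bias the Group 1 v Group 2 comparison, mainly for pain, vertigo and otitis media.

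The size cannot be derived from the plan. Across the partial-attribution cases shown, false differences run from 0.7% to 28% of trials, against 0.9% to 2.6% when all events are counted. At a 10% background rate the effect is small or absent; at 20% to 30% with strong asymmetry it is substantial. These figures rest on assumed background rates, attribution rates and test.

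The documents do not show that unblinded staff will certainly apply the label, nor that Group 1 can contribute no related events. Complete recovery, the primary outcome in section 11, is unaffected. The change is worth making before data collection, because complaints screened out as unrelated may not be recoverable evenly in both arms.

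**What to change.** Define the compared safety end point as all adverse events, regardless of judged relationship to treatment. Compare Groups 1 and 2 on the number of participants with any event and with each event listed in section 10, Assessment of Safety (pain, bleeding, vertigo, otitis media, perforation). Record these from the review of systems and head and neck examination already planned for every visit, with the same questions in both arms. Give investigator-judged relatedness as a supportive listing only, and state who judges it. Align the wording of the study question, the end-point list and the visit instruction.

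The cost is a short common adverse-event checklist at existing visits, plus some background noise from unrelated events. It removes the attribution step but not reporting bias: patients know whether they were injected and may still report symptoms differently.

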After obtaining consent, the study participant will undergo a complete history, head, neck, and cranial nerve exam. Facial function will be evaluated with House-Brackmann (H-B) scoring system. For participants with a high suspicion of Lyme disease based on history, Lyme disease serology will be drawn. Electroneurography (ENoG) and electromyography (EMG) testing will be performed on patients with complete facial nerve paralysis. Every participant will be treated with oral steroids (prednisone 60 mg for 5 days followed by a 5 day taper), unless they are unable to for medical reasons.

The study participants will then be randomized into the control group or the treatment group. If randomized to the treatment group, the patient will undergo one intratympanic steroid injection every 3-4 days over the course of 3 weeks for a total of 3 injections. A third group of patients will include those patients that are unable to take oral steroids for medical reasons (such as diabetes); these patients will only receive the intratympanic injection. An audiogram and tympanography testing will be performed on patients that are randomized to receive an intratympanic injection (Group 2) or are placed in Group 3 for medical reasons.

3. Abbreviations

All abbreviations will be defined in parenthesis following their first occurrence in the text.

4. Background Information

Facial nerve paralysis is due to inflammation surrounding the facial nerve. Current clinical practice guidelines for treatment of facial nerve paralysis recommend a 10 day course of oral steroids +/- oral acyclovir. Treatment should begin within 72 hours of symptom onset. In patients with complete facial paralysis, electrodiagnostic testing should be offered to the patient (1-2). In patients with 90% degeneration on electroneuronography (ENoG) testing, facial nerve decompression may be considered but is not a current recommendation.

In 1973, Bryant reported on ten cases where intratympanic steroid injection was used for the treatment of Bell's palsy (3). All but one of these patients had complete recovery of their facial nerve function. The remaining patient had 75% recovery. None of these patients suffered complications from the injections. The next study published on intratympanic steroid injection

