Protocol: *Facial Nerve Study*

PI: [name]

Exclusion Criteria:

1. Another cause of facial nerve paralysis that is not idiopathic
2. Otologic disease including otitis media, temporal bone fracture, a previous history of facial nerve palsy in either side, history of otologic surgery, and suspected Ramsay Hunt syndrome.
3. Systemic disease including history of tuberculosis, history of head and neck cancer, other neurological disorders, recent use of ototoxic medications, liver or renal dysfunction, and other illnesses that would contraindicate the use of high-dose steroid therapy.
4. Pregnancy

Withdrawal Criteria:

Subjects may withdraw from the study at any time without prejudice to their care. They may also be discontinued from the study at the discretion of the Investigator for lack of adherence to study treatment or visit schedules or adverse events. The Investigator may also withdraw subjects who violate the study plan, or to protect the subject for reasons of safety or for administrative reasons. It will be documented whether or not each subject completes the clinical study. If the Investigator becomes aware of any serious, related adverse events after the subject completes or withdraws from the study, they will be recorded in the source documents and on the case report form.

8. Treatment of Subjects

Participants in Groups 1 & 2 will be treated with steroids (prednisone 60 mg for 5 days followed by 5 day taper) as defined by the current standard of care. Patients in Group 1 will not have any further treatment. Patients in Group 2 & 3 will undergo intratympanic steroid injection. The patient will undergo one injection every 3-7 days over the course of 3 weeks for a total of 3 injections.

9. Costs

Participants will not be paid to be a part of the study. Subjects will be responsible for the normal cost of treatment associated with facial nerve paralysis, including any tests that the physician feels are necessary and all medications. Subjects who are randomized to one of the groups to receive the intratympanic injections will not be responsible for the added costs of the injection (which include the medication and phenol), the audiogram and tympanometry, and extra office visits to receive each injection.

10. Assessment of Efficacy

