The integrity of the data collected will be maintained by the randomization of trial subjects to their groups (*control vs. treatment*). All subjects are being treated using standard protocols. Even though participants will not be fully blinded, the data collected is reliable because it is randomized and objective measures will be obtained. Objective measures for this study include complete recovery of facial nerve function, time to complete recovery of facial nerve function, improvement of facial nerve function within 3 weeks, and time to initial improvement of facial nerve function. The University's biostatistics group can view any data collected prior to publication.

14. Ethics

A randomized study involving the adult population is subject to ethical as well as scientific considerations. The patients will not be blinded because it is unethical to perform a sham procedure. HIPAA guidelines will be followed in order to protect the privacy of study participants. The Otolaryngology community stands to benefit significantly from this study, as results will potentially yield information which will be used to improve outcomes of patients with facial nerve paralysis as this can be a debilitating disease process.

15. References

3. Bryant FL. Intratympanic injection of steroid for treatment of facial paralysis. *Laryngoscope.* 1973 May;83(5):700-6. PubMed PMID: 4702471.

Protocol: *Facial Nerve Study*

PI: [name]

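### Follow-up visits and blinded videos are counted from the end of treatment and no time zero is stated, so on several readings the 3-week and initial-improvement end points are read on different days by arm

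*Combined protocol and SAP*

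**What the plan says.** **Visit anchor.** Section 6 (Follow-Up) states: "Patients will be evaluated once a week for the first month after completion of treatment". Visits are then monthly. Section 6 (Procedures) repeats this anchor, but a separate sentence there brings Group 1 back weekly for a month without saying from when.

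**Treatment length.** Groups 1 and 2 take prednisone for 5 days plus a 5-day taper. Section 8 adds: "Patients in Group 1 will not have any further treatment". For Group 2, section 2 specifies "one intratympanic steroid injection every 3-4 days over the course of 3 weeks for a total of 3 injections", while section 6 (Procedures) says "There will be one injection every 3-7 days over the course of 3 weeks for a total of 3 injections"; section 8 also gives 3-7 days. Completion of treatment is not defined for either arm.

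**Which scores count.** Under Assessment of Efficacy, blinded raters "will determine the efficacy by evaluating each individual study subject via video recording". Section 6 (Procedures) lists recordings before treatment and at follow-up visits after treatment; injection visits are not listed. Section 5, however, says patients will be "examined and scored using House-Brackmann scoring system by a blinded investigator trained in otolaryngology", and section 6 has an H-B score taken at every clinic visit. Group 2 has "extra office visits to receive each injection" (section 9), which Group 1 does not.

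**End points.** Section 13 counts among the objective measures that support the reliability of the data "improvement of facial nerve function within 3 weeks, and time to initial improvement of facial nerve function". No section says from which day these, or time to complete recovery, are counted.

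**The concern.** An improvement can be dated only to a visit at which the face is scored. If the two arms are scored on different days after randomisation, identical patients get different recorded improvement times and different 3-week results. Two of the four efficacy end points are exposed. The sign and size of any artefact depend on three things the plan leaves open: time zero, the day treatment is complete in each arm, and whether scores at injection visits count. If these are settled after data are seen, the choice itself can move the result.

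**Working it through.** The plan gives no figure on this point, so there is none to reproduce. The check is day arithmetic followed by an illustration.

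**Step 1: completion days.** Day 0 is randomisation and first prednisone dose (assumption).
- Group 1: 5 + 5 = day 10.
- Group 2: the later of day 10 and (first injection day + 2 × interval).
  - First injection on day 0, 3-4 day interval: third injection on day 6-8, so completion is on day 10.
  - First injection on day 0, 7-day interval: 0 + 2 × 7 = day 14.
  - Day 21 arises only if injections start late (7 + 2 × 7 = 21) or are spread to fill the stated 3 weeks.

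**Step 2: video days.** The first follow-up video is 7 days after the anchor, then weekly.

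| Group 1 anchor | Group 2 completes | First video, Group 1 v 2 | Last video by day 21, Group 1 v 2 |
|---|---|---|---|
| day 10 | day 10 | 17 v 17 | 17 v 17 |
| day 10 | day 14 | 17 v 21 | 17 v 21 |
| day 0 | day 10 | 7 v 17 | 21 v 17 |
| day 0 | day 14 | 7 v 21 | 21 v 21 |

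The day-0 anchor is the other possible reading of the Group 1 sentence in section 6. The first video differs by arm in three of these four calendars, and the last video by day 21 in two. This step needs no distribution.

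**Step 3: time to initial improvement with no treatment effect.** Assumptions, none from the documents: lognormal times, log-SD 0.5, medians 10/14/21 days, 95% eventually improve, 30 per arm, clock from randomisation, each event dated to the first scored visit at or after it, two-sided 5% log-rank test (section 11 names no test). Percentage of trials falsely significant:
- Completion 10 v 10, videos only: 7/5/5.
- Completion 10 v 14, videos only, exact visit days: 93/39/8, against the injection at medians 10 and 14. With log-SD 0.7: 74/31/8.
- The same with up to 3 days of scatter around each visit: about 65/20/5.
- Completion 10 v 14, with injection-visit scores on days 7 and 14 also used: 75/19/6, now in favour of the injection at medians 10 and 14; about 30/9/5 with scatter.
- Group 1 visits from randomisation, Group 2 injected on days 0, 7 and 14, injection-visit scores used: 5/6/10.
- Same assessment days in both arms: 5/4/5.

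**Step 4: 3-week end point, clock from randomisation.** P(improved by day d) = 0.95 × Φ(ln(d/median)/0.5). At median 14:
- Day 17: ln(17/14)/0.5 = 0.388, Φ = 0.651, P = 0.619.
- Day 21: ln(21/14)/0.5 = 0.811, Φ = 0.791, P = 0.752.
- Difference: 13 points.

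Across medians 10/14/21, day 17 gives 81/62/32% and day 21 gives 88/75/48%, a difference of +7/+13/+16 points for Group 2. Fisher's test rejects in 5/13/16% of trials, against 2-3% when both arms are read on day 17. If Group 1's visits start at randomisation and Group 2 completes on day 10, the sign reverses.

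**Step 5: what analysis alone can do.** An interval-censored likelihood-ratio test on the 10 v 14 video visits rejects in 8/5/3% (lognormal model) or 5/6/6% (Weibull). It cannot supply a day-21 reading that was never taken.

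**Step 6: complete recovery.** With 85% recovering (assumed), moving the 12-month limit from day 375 to day 386 (10 + 365 and 21 + 365) changes the proportion by 0.85 × [Φ(ln(386/m)/SD) − Φ(ln(375/m)/SD)]. The largest value, at median 56 days and SD 0.7, is 0.0003, or 0.03 points.

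**The case against.** The strongest reply is that the documents show missing wording, not a biased schedule. If both arms complete on day 10, Group 1's visits run from completion and only videos count, the calendars are identical. If Group 1 is seen weekly from randomisation, Group 2 is injected on days 0, 7 and 14 and injection-visit scores count, both arms are scored on days 7, 14, 21 and 28. This stands: the concern is conditional. But the plan does not select either reading, and applying its stated anchor with a 7-day interval separates the arms.

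The illustration also assumes a test and, in its largest figures, exact attendance. That stands too. Scatter lowers the rates, and at median 21 with 10 v 14 they are close to nominal.

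Using injection-visit scores has thinner support than videos, because the efficacy section points to video. The reversed direction therefore shows what the wording leaves open, not what was intended.

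A reader might go further and infer three things that the documents do not support:
- **That Group 2 completes on day 21.** With intervals of at most 7 days, the third injection falls at most 14 days after the first, so day 21 needs a late start or wider gaps. The more extreme error rates that calendar gives should not be the headline.
- **That a timing artefact could not be told from an effect.** For the time-to-event end points, actual visit dates and an interval-censored analysis largely separate the two. Only the 3-week end point is beyond such repair.
- **That the 3-week end point is distorted whatever the clock.** Counted from completion, 10 v 14 reads day 31 v 35; the differences are +0.5/+2/+6 points and Fisher's test rejects in only 0.3/1.1/4.7% of trials.

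**Conclusion.** The point holds in conditional form and should be fixed. The plan anchors visits and blinded videos to an undefined, possibly arm-specific day and states no time zero. On several readings, time to initial improvement and the 3-week end point can then differ by arm with no treatment effect. For completion on day 10 v 14, clock from randomisation and videos only, false significance for initial improvement ranges from near nominal at a median of 21 days to about 65% (scattered visits) or 93% (exact visits) at a median of 10 days. The 3-week difference is 7 to 16 points. These sizes rest on the assumed day 0, lognormal times, log-SD of 0.5, 30 per arm and tests; the unequal visit days rest only on the assumed day 0 and the stated intervals.

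The scope is limited. Neither of the two end points is among the three questions in section 5. It would be wrong to infer that the primary result is compromised: complete recovery moves by at most 0.03 points. Time to complete recovery shares the missing time zero, but with 10 v 14 counted from randomisation its false-positive rate is only 6/8/9% at assumed medians of 28/42/56 days.

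**What to change.** State in sections 6 and 11:
- Time zero for the 3-week end point and both time-to-event end points is the day of randomisation.
- Groups 1 and 2 are assessed on the same days counted from randomisation (for example weeks 1, 2, 3 and 4, then monthly to H-B I or the follow-up limit), with a video for blinded rating at each.
- Only these visits enter the between-group efficacy comparison. An injection visit that falls on an assessment day may serve if the video is recorded.
- The time-to-event end points are analysed with a grouped or interval-censored method.

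Keep the treatment-anchored safety checks: perforation at 14 days and 1 month, and the audiogram and tympanogram about 1 month after the third injection.

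The investigators must also reconcile the injection-interval wordings (sections 2, 6 and 8), the start of Group 1's weekly visits (section 6), the follow-up limits (section 2 counts 12 months from completion; section 6 gives one year with no anchor), and whether blinded scoring is by video only (section 5, section 6 and Assessment of Efficacy). No injection schedule is proposed here.

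**Cost.** Protocol wording; a few extra recordings; possibly one or two short extra visits per Group 2 patient in weeks 1-3 when no injection is due; and possibly one safety visit that no longer coincides with an efficacy visit. For example, one month after a day-14 completion is about day 44, between week 4 (day 28) and the next monthly visit (about day 58). The sample size does not change.
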